2.6.3.11 Sensitivity analysis

We will conduct the following sensitivity analysis subject to contractual agreement. We will test the sensitivity of the results of the physical activity and diet primary outcomes to alternative methods of missing data management (multiple imputation and delta adjustment).

Simple imputation:

- **Physical activity**: Within each combination of data collection point (baseline, 1 month, 3 months, 5 months), treatment arm (no / low / medium / high incentives) and day of the week, for reads based on at least 6 hours of wear-time, we will identify the 2.5th and 97.5th percentiles for each physical activity outcome. We will replace reads below this 2.5th percentile (no matter what their wear-time is) with the 2.5th percentile. Similarly, we will replace reads above the 97.5th percentile with the 97.5th percentile. This means we can use a full dataset among non-attrited participants with minimal assumptions around the structure of missing data.
- **Diet**: Within each combination of data collection point, treatment arm and gender, we will replace values of each primary diet outcome below the 1st percentile with the 1st percentile, and values above the 99th percentile with the 99th percentile. We will still exclude administrations that fail any of our attention checks (e.g. completion time of under 3 minutes).

Multiple imputation: If the results differ between the main specification and the simple imputation method above, we will perform multiple imputation with delta adjustment sensitivity analysis.

• **Physical activity**: Having replaced invalid daily reads within the measurement week using valid reads from up to two weeks before/after, we will generate *n* imputed datasets, where *n* is the percentage of incomplete cases rounded up

to the nearest integer (following the rule of thumb suggested by Bodner (2008)⁶¹ and White et al. (2011)⁶²). We will use sequential predictive mean matching to impute missing values of physical activity outcomes within each dataset (imputing the outcomes together). As predictors, we will use other reads in the measurement week, all covariates in the main specification, and household- and person-level fixed effects.

We will perform multiple imputation only for the sample of individuals who have at least one valid read in the measurement week. We will then estimate the following equation on each imputed dataset for a range of (fixed) Δ :

(3)

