2.6.3.2 Missing data management

Missing data might occur when a user stops providing data temporarily or permanently. We suggest two different procedures to handle missing data depending on whether participants stop providing data temporarily or permanently:

⁵³ Crutzen, R., Viechtbauer, W., Spigt, M., & Kotz, D. (2015). Differential attrition in health behaviour change trials: A systematic review and meta-analysis. *Psychology & Health*, *30*(1), 122–134. doi: 10.1080/08870446.2014.953526

⁵⁴ Schmidt, S. C. E., & Woll, A. (2017). Longitudinal drop-out and weighting against its bias. *BMC Medical Research Methodology 2017 17:1, 17*(1), 1–11. doi: 10.1186/S12874-017-0446-X

- User stops providing data **temporarily**. For example, PA data may not be available on a given date, or a user provides only one Intake24 recall at a given data collection point. In the sections below, we outline how we would approach such circumstances.
- User stops providing data **permanently** (attrition from measurement). Our general principle is that we will not attempt to replace missing values when missing outcome measures are due to attrition (i.e. a user does not provide any data after a given data collection point in the trial). We define this type of missing data as 'attrition', and we detailed our approach to deal with differential attrition in the previous section.

Physical activity outcomes

For physical activity outcomes (MVPA, steps, energy expenditure), we will get daily reads from the date of onboarding to the end of the trial. It is possible that a user does not provide data on a given day for the following reasons:

- Forgetting to wear the wearable;
- Dead battery.

Individuals may also wear the wearable device on a given day but not long enough for the reading to be sufficiently accurate. We define a 'valid' read as occurring when the individual wears their wearable device for at least 6 hours in the day. Users will not be nudged to meet this criteria, but will be nudged to wear their device as long as possible each day. In the main specification for each physical activity outcome, we use 'valid' reads for all days of the 21st week (i.e. month 5) of the trial as outcomes, and also control for 'valid' reads taken in the last 7 days of the baseline period if they exist.

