This imputation process will increase the sample size of person-day observations for the 5-month measurement week, which increases the precision of our estimates. It will also remove (i) reads based on low wear-time which may be underestimating physical activity, as well as (ii) reads that are erroneous due to malfunctioning wearable devices. This imputation process may not fully mitigate the issue that users will be more likely to wear the device when doing more PA (likely to be affected by the treatment assignment). However, we do not think this relationship will be too strong near the 6-hour cut-off point, since historical data on HUL Delta⁵⁷ users suggests that few users (<3%) wear the wearable for less than 6 hours per day on average. Alternative imputation methods that we have considered such as multiple imputation, which takes advantage of the within-subject auto-correlation over time does not fully mitigate against this issue either.

Dietary outcomes

Dietary recalls are provided by users only at key data collection points (baseline, 1 month, 3 months, 5 months). At these data collection points, users are encouraged to provide two recalls in the same week. We do not impute dietary outcomes. If a user provides one dietary recall at a given data collection point, we will not impute the other. If a user provides zero dietary recalls at a given data collection point, we will not impute the not impute either of the recalls since this requires using information that is at least 2 months away.

⁵⁶ The following example provides further clarification. Say that an individual has an invalid read from Monday 16th May, which is at month 5, i.e. 21st week into the trial after randomisation.

[•] If they have a valid read from Monday 9th May or Monday 23rd May, we will take this as the value for Monday 16th May. If they have valid reads for both dates, we will average them.

[•] If they do not have a valid read from Monday 9th May or Monday 23rd May but do have a valid read from Monday 2nd May or Monday 30th May, we will average the available reads from these dates.

[•] If they do not have a valid read from 2nd, 9th, 23rd or 30th May, we will not impute.

⁵⁷ HUL Delta is the name of HUL's own branded wearable device.

For both the primary physical activity and dietary outcomes, we examine the sensitivity of our main findings to different assumptions about missing data (see section 2.6.3.9).

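### The physical-activity simple-imputation check counts short wear as low activity, so a wear gap between arms can enter as a treatment difference; it should not decide whether multiple imputation runs

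*Protocol*

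**What the plan says.** Protocol 2.6.3.2 sets the main rule for physical activity: "We define a 'valid' read as occurring when the individual wears their wearable device for at least 6 hours in the day". Shorter-wear reads are replaced from neighbouring weeks where possible and otherwise left out. One reason given is to remove "reads based on low wear-time which may be underestimating physical activity". The same section concedes a weakness that this may not fully cure, namely that "users will be more likely to wear the device when doing more PA (likely to be affected by the treatment assignment"). It plays the concern down because, in historical data, "few users (<3%) wear the wearable for less than 6 hours per day on average".

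Protocol 2.6.3.11, repeated in Appendix D2, sets the first sensitivity check. Its cut-offs are set separately by collection point, arm and day of week, using valid reads only: "for reads based on at least 6 hours of wear-time, we will identify the 2.5th and 97.5th percentiles for each physical activity outcome". Then comes the replacement step: "We will replace reads below this 2.5th percentile (no matter what their wear-time is) with the 2.5th percentile". High reads are lowered to the upper cut-off in the same way. The stated benefit is: "This means we can use a full dataset among non-attrited participants with minimal assumptions around the structure of missing data".

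The check also works as a switch: "If the results differ between the main specification and the simple imputation method above, we will perform multiple imputation with delta adjustment sensitivity analysis". All of this is subject to contractual agreement.

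**The concern.** The cut-offs come from valid reads but are applied to all reads, and no step removes the short-wear ones. A day with two hours of wear that still records more than the floor is kept as if it were a full day. A day that records less is raised only to the bottom of the valid range in that arm. The main specification discards the same reads because they understate activity.

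The protocol links wear to activity and activity to treatment assignment, so unequal wear between arms is foreseeable. Step and activity-minute challenges carry rewards in the incentive arms only (2.3.1.1), which gives those users a reason to wear the tracker that controls lack. More short-wear days in control would lower the control mean under this rule and favour the incentive arms.

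What is at stake is how the robustness check is read. Agreement or disagreement with the main result may reflect wear compliance, and that comparison alone decides whether multiple imputation with delta adjustment is carried out.

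**Working it through.** **1. The plan's yardstick.** Section 2.4.1 gives a minimum detectable effect of 371 steps/day. The inputs are SD 4,096, 2,100 control against 2,100 pooled incentive, baseline correlation 0.5, ICC 0.3, 80% power and Bonferroni for two outcomes (a two-sided overall 5% is assumed). The household shares 39/41/20% are read as shares of participants, as in Appendix B's example.

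- Design effect = 1 / (0.39 + 0.41/1.3 + 0.20/1.6) = 1.204
- (2.241 + 0.842) × 4,096 × √(1 − 0.5²) × √1.204 × √(2/2,100) ≈ 370

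The plan's figure reproduces. With a design effect from the mean household size, 1 + 0.81 × 0.3 = 1.243, the result is 376.

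**2. Simple form of the bias.** False difference = (gap between arms in the share of low-wear days) × (mean valid read − mean value entered for a low-wear day).

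The document gives no mean for steps, so 7,000 is assumed, with a gamma distribution and the plan's SD used as a day-level SD. The 2.5th percentile is then about 1,400. If every low-wear day entered at that floor, each percentage point of gap would give 0.01 × (7,000 − 1,400) = 56 steps. Over assumed means of 5,000 to 9,000 the range is 46 to 62. For MVPA, over assumed means of 20 to 50 min, the same formula gives 0.20 to 0.37 min/day per point.

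**3. Simulation with no true effect.** Two million person-days per arm were simulated. Half of the low-wear days were unworn and the rest recorded 0 to 40% of the day's activity (both assumed). Where wear depends on activity, the chance of low wear was made proportional to exp(−steps/4,000), also assumed. Entries are incentive minus control in steps/day, with a standard error of about 4,096 × √(2/2,000,000) ≈ 4.

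| Setting | Low wear, control/incentive 5/3% | 10/5% | 20/10% |
|---|---|---|---|
| Rule as written, wear independent of activity, unworn days carry a read | +105 | +265 | +534 |
| Same, but unworn days carry no read | +50 | +133 | +296 |
| Rule as written, low wear on less active days, unworn days carry a read | +56 | +129 | +220 |
| Same, but unworn days carry no read | −10 | +2 | −24 |
| Caps on valid reads only, low wear on less active days | −59 | −156 | −364 |

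Caps on valid reads only, with wear independent of activity, stay within about 6 steps of zero at every gap.

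**4. Per percentage point.** The gaps are 2, 5 and 10 points.

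- Row 1: 105/2, 265/5 and 534/10, about 53 each.
- Row 2: 50/2, 133/5 and 296/10, which is 25 to 30.
- Row 3: 56/2, 129/5 and 220/10, which is 22 to 28.
- Row 4: about zero.

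As a check on row 1, low-wear days entered at about 1,635 on average against about 6,930 for capped valid reads, and 0.01 × (6,930 − 1,635) ≈ 53.

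**5. Against the yardstick.** A 5-point gap gives 265/371 = 71% of the detectable effect in row 1, 133/371 = 36% in row 2 and 129/371 = 35% in row 3.

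**The case against.** Several points on the other side stand.

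- **It is a sensitivity analysis.** It is subject to contractual agreement, and the main specification does not use reads under 6 hours. A reader might infer that the primary result is biased by this rule; it is not.
- **A check that drops the wear filter is a legitimate contrast.** The main result depends on that filter, so bringing back short-wear reads tests something useful. What fails is the description and the switch.
- **The switch often opens.** If the main result is near zero and the rule gives +265, the results differ and multiple imputation runs. A reader might infer that the check will confirm a false positive. That needs a main result already wrong by a similar amount, and nothing in the document shows this.
- **Near-zero activity is too strong.** A reader might infer that unworn days enter as almost no activity. The step floor is about 1,400 under the assumptions used. An MVPA floor of exactly zero would need a share of zero-minute days that the document does not give. Nor does the protocol say whether an unworn day counts as a read. The claim of a full dataset suggests that it does, but 2.6.3.2 separates days without data from days worn too briefly.
- **Capping valid reads only is not a neutral cure.** A reader might infer that it removes the bias. It does so only if wear is independent of activity. If low wear falls on less active days, as 2.6.3.2 suggests, it is biased in the opposite direction by as much or more (last row of the table).
- **Low wear may be rare.** The figure of under 3% points that way, but it concerns users' averages in historical data. It does not count person-days and is not split by arm.

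**Conclusion.** The point holds in a limited form. The rule returns reads that the protocol itself calls invalid and gives them low values, so the claim of minimal assumptions is wrong. Where wear differs by arm, part of that difference can appear as a treatment difference, and it favours the incentive arms if they wear the tracker more.

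Under the stated assumptions the size is about 25 to 50 steps/day per percentage-point gap when wear is independent of activity. It is smaller, and can be near zero, when low wear falls on less active days. The mean, the wear gaps, the split of unworn and briefly worn days and the link between wear and activity are all assumed, because the document does not give them. The primary estimate is not affected. The practical fault is that a check this sensitive to wear compliance decides alone whether the better-suited analysis is done.

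**What to change.** For the physical-activity outcomes, in both 2.6.3.11 and Appendix D2:

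1. Delete the sentence claiming a full dataset with minimal assumptions.
2. Keep the rule if wanted, but label it as a scenario in which short wear means low activity, and state that its bias can favour the incentive arms.
3. Remove the condition that multiple imputation runs only if this check differs from the main result. Run the planned multiple imputation with delta adjustment regardless, with reads under 6 hours treated as missing.
4. Optionally report a version that caps only reads with at least 6 hours of wear alongside it, noting that this version is itself biased if wear depends on activity.

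The cost is a change of wording in two places and a little more analysis work. No extra data are needed.

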2.7 Monitoring

2.7.1 Data monitoring

Throughout the trial period, HUL will monitor data on 'consented users' daily and share these data with BIT and DHSC via a live dashboard. As noted above, information about recruitment rate and attrition might be used to inform decisions by HUL and DHSC to potentially increase the resources and efforts allocated to the marketing campaign or to retain users to achieve the target sample size at various trial stages.

⁶¹ Bodner, T. E. (2008). What improves with increased missing data imputations? *Structural Equation Modeling: A Multidisciplinary Journal* (15) 651-675.

⁶² White, I. R., Royston P. and Wood A. M. (2011). Multiple imputation using chained equations: Issues and guidance for practice. *Statistics in Medicine* (30) 377-399.

⁶³ Rubin, D.B. (1987). Multiple Imputation for Nonresponse in Surveys. New York: John Wiley & Sons, Inc.

We do not plan to conduct any interim quantitative analysis for outcomes prior to the completion of the data collection period for the longest follow up. We do not plan to discontinue the study depending on numbers of active users, as many questions in this study pertain to retention and engagement levels over the course of the intervention. While this is a short-term trial with minimal risks of harm we will nonetheless set up an independent data monitoring committee (DMC)⁶⁴ to be convened on an ad hoc basis to investigate un-blinded safety and data issues, or to investigate issues raised by the Trial Steering Committee.

Table 13 provides an overview of the different kinds of reporting that DHSC will receive throughout the duration of the trial and after the trial is concluded.

Trial phase	Monitored data (n)	Reporting frequency	Provided by whom?	In which form
MARKETING: ACQUISITION & ENGAGEMENT (Intervention period)	 Funnel report (vs. target) Registered Consented Randomised 	Daily (during launch) Weekly thereafter	HUL	Live dashboard
	 Participant recruitment profile report (aggregate level only) – profile of registered users by: Trial arm Age Gender Suburb / top-level postal code Ethnicity Sub-group segmenters where populated – refer to DPIA for full list of attributes for segmentation Week, month, cumulative 	Daily (during launch) Weekly thereafter	HUL	
	Device connect type	Daily	HUL	
PERFORMANCE REPORTING (Intervention period)	 DAU / WAU / MAU by: Trial arm Age Gender Suburb / top-level postal code Sub-group segmenters (disability status, ethnicity, self-motivation, etc.) – refer to DPIA for 	Weekly	HUL	Live dashboard

Table 13. Monitoring report by trial phase (TBC)

⁶⁴ Chan AW, Tetzlaff JM, Gøtzsche PC, Altman DG, Mann H, Berlin JA, Dickersin K, Hróbjartsson A, Schulz KF, Parulekar WR, Krleža-Jerić K. SPIRIT 2013 explanation and elaboration: guidance for protocols of clinical trials. Bmj. 2013 Jan 9;346.

	 full list of attributes for segmentation Week, month, cumulative Surveys completed + results In-app surveys Intake24 CS report: # tickets received # tickets resolved # pending SLA performance vs. target CSAT Uptime SLA reporting (monthly %) 	Weekly / monthly / YTD Weekly Fortnightly Monthly	HUL	Live dashboard
INCENTIVES REPORTING (Intervention period)	 Incentives report, by: Trial arm Age Gender Suburb / top-level postal code Sub-group segmenters (disability status, ethnicity, self-motivation, etc.) – refer to DPIA for full list of attributes for segmentation Week, month, cumulative Points earned Points unredeemed (%) Quantity, £ value, and number of incentives redeemed, by: Product category Retailer / manufacturer Physical / virtual SKU Top 20 most popular redemption items by volume Value of incentives issued Mean time between incentive issue to incentive redemption 	Monthly (refer to HUL's design plan)	HUL	Live dashboard
HEALTH & BEHAVIOUR CHANGE REPORTING (Intervention period)	 Health dashboards, by: Trial arm Age Gender Deprivation index Sub-group segmenters – refer to DPIA for full list of attributes for segmentation 	Daily	HUL	Live dashboard

	 Baseline report Weight report: BMI Sleep report: Median daily sleep duration Median daily sleep efficiency Monthly health changes report: Starting sleep vs. Tn sleep Starting steps vs. Tn steps Starting moderate / intense physical activity vs. Tn moderate / intense physical activity Challenges report: Challenges report: Challenges started Challenge status: overachievement success, almost success, failure Challenge validation status (% of rejection?) Recommended and chosen challenge difficulty: maintain or harder Type of challenges (e.g. % of users selected "Step Up", "Boost veggie and fruits") 	Monthly	HUL	Live dashboard
Post trial - 12 weeks after the end of the trial (incl. end of qualitative research components)	All primary, exploratory, quantitative IPE, and qualitative IPE outcomes described in this protocol	Once (final report)	BIT	Report

2.7.2 Harms

The intervention tested in this study is considered to be a low-risk health promotion intervention. However, unintended consequences (both positive and negative) will be explored as part of the qualitative interviews and focus groups conducted as part of the Implementation and Process Evaluation. As specified in section 4.3.6, participants reporting negative unintended consequences during the interviews will be signposted to relevant resources. We will have a clinical safety group in place throughout the pilot, as well as a Clinical Safety Officer (CSO) to monitor (potential) harms during the study. Participants will be informed at the consent stage that they are free to stop participating in the study at any point, without having to provide any reason.

2.7.3 Auditing

Auditing involves periodic independent review of core trial processes and documents.⁶⁵ For this trial, we do not plan any auditing. The trial will be conducted according to the processes described in this protocol. The study protocol has been designed with input and guidance from the DHSC's policy and delivery team and the Design and Evaluation Advisory Group (DEAG – the group of experts from across DHSC diet and physical activity policy and National Institute for Health Research Policy Research Units, established to provide support, advice and steers on the development of the design plan and evaluation protocol). The protocol will subsequently be going through external peer review before being submitted to UKHSA for ethical approval.

The trial will only be launched following ethical approval from UKHSA. The UKHSA ethics committee and the publicly available protocol will be updated should there be any changes to the intervention or study processes taking place after the launch of the study.

3. Ethics and dissemination

The study has obtained ethical approval from UKHSA⁶⁶.

Before the trial launch, BIT will register the evaluation protocol on an appropriate registration platform, to be agreed with the funder, DHSC.⁶⁷

The UKHSA ethics committee, the funder (DHSC), and the publicly available protocol will be updated should there be any changes to the intervention or study processes taking place after the launch of the study.

⁶⁵ Chan AW, Tetzlaff JM, Gøtzsche PC, Altman DG, Mann H, Berlin JA, Dickersin K, Hróbjartsson A, Schulz KF, Parulekar WR, Krleža-Jerić K. SPIRIT 2013 explanation and elaboration: guidance for protocols of clinical trials. Bmj. 2013 Jan 9;346.

⁶⁶ An update will be provided on this approval in December 2022.

⁶⁷ The trial was registered with ISRCTN with Submission number 43198 ahead of the trial launch.

Subject to DHSC's approval, it is BIT's intention to publish the results from this study in an academic journal. Subject to DHSC's approval, results of the trial might also be presented at conferences, public meetings, or through other platforms.

4. Implementation and Process Evaluation

